## 7. ADVERSE EVENTS

### 7.1. Definitions

The definitions below are based on International Council for Harmonization (ICH) guideline E2A, “Clinical Safety Data Management: Definitions and Standards for Expedited Reporting.”

#### 7.1.1. Adverse Event

An AE is any untoward medical occurrence in a subject or clinical trial subject administered a pharmaceutical product that does not necessarily have to have a causal relationship with this treatment. An AE can therefore be any unfavorable and unintended sign (including an abnormal laboratory finding), symptom, or disease temporally associated with the use of a medicinal product, whether or not related to the medicinal product.

- AEs may be new events.
- AEs may be preexisting events that increase in frequency, severity, or change in nature or seriousness during or as a consequence of participation in clinical studies.
- AEs may be pre- or posttreatment complications that occur as a result of a protocol-mandated procedure (such as a biopsy).
- AEs may be clinically significant changes from baseline in physical examination, laboratory tests, or other diagnostic investigation (e.g., laboratory results, x-ray findings).
- AEs may result from an overdose of the study medication.

Whenever possible, the diagnosis (rather than a series of terms related to a diagnosis) should be recorded as the AE term.

An AE does not include the following:

- Medical or surgical procedures (such as surgery, endoscopy, tooth extraction, or transfusion); the condition that leads to the procedure is an AE
- Pre-existing diseases or conditions present or detected before signing an informed consent form that do not worsen
- Situations where an untoward medical occurrence has not occurred (such as hospitalization for elective surgery or social and/or convenience admissions)
- Overdose of either study medication or concomitant medication without any signs or symptoms, unless the subject is hospitalized for observation

Any medical condition or clinically significant laboratory abnormality with an onset date prior to the time the subject signed the informed consent form is considered to be preexisting and should be documented in the medical history CRF.

Pregnancy is not an AE; however, if a female subject becomes pregnant during the conduct of the study, the sponsor will be notified according to the procedures for SAE reporting as outlined in Section 7.4.3. Follow-up information regarding the outcome of the pregnancy and any fetal or neonatal sequelae will be obtained and documented.

### 7.1.2. Serious Adverse Event

A serious adverse event (SAE) is defined as any untoward medical occurrence occurring at any dose that results in any of the following outcomes:

- Death
- Life-threatening situation. “Life threatening” refers to a situation in which the subject was at risk of death at the time of the event; it does not refer to an event which might have caused death if it were more severe.
- Inpatient hospitalization or prolongation of existing hospitalization  

Note: “Inpatient hospitalization” means the subject has been formally admitted to a hospital for medical reasons, for any length of time. This may or may not be overnight. It does not include presentation and care within an emergency department. A scheduled hospitalization for a preexisting condition that has not worsened during participation in the study does not meet this criterion. Preplanned hospitalizations for an elective medical/surgical procedure, scheduled treatments, or routine check-ups do not meet this criterion. Complications that occur during hospitalizations are AEs. If a complication prolongs hospitalization, it is an SAE.
- Disability- A persistent or significant incapacity or substantial disruption of the ability to conduct normal life functions
- Congenital anomaly/birth defect in the offspring of a subject who received study medication
- Important medical events that may not result in death, be immediately life threatening, or require hospitalization, may be considered an SAE when, based upon appropriate medical judgment, they may jeopardize the subject and may require medical or surgical intervention to prevent one of the outcomes listed in this definition. Examples of such events are as follows:
  - Intensive treatment in an emergency room or at home for allergic bronchospasm
  - Blood dyscrasias or convulsions that do not result in hospitalization
  - Development of drug dependency or drug abuse

### 7.1.3. Additional Considerations for Serious Adverse Events

- Death is an outcome of an AE and not an AE in itself. Deaths of unknown cause for which the Investigator cannot identify a cause of death will be captured as death of unknown cause or death not otherwise specified.
- All deaths, regardless of cause, must be reported for subjects if the death occurs while the subject is participating in the study.
- “Occurring at any dose” does not imply that the subject is receiving study medication at the time of the event; dosing may have been given as treatment cycles or interrupted temporarily before the onset of the SAE but may have contributed to the event.

#### 7.1.4. Adverse Event of Special Interest

- At each study visit, the Investigator (or designee) will specifically query for any AESIs. The following events are considered AESIs for this study:
  - Supine hypertension
  - Cardiovascular events (myocardial infarction, cerebrovascular accident, cardiac arrhythmia, congestive heart failure)
  - Convulsion
- All AESIs must be reported to Sponsor Clinical Safety and Pharmacovigilance within 24-hours of awareness by the Investigator or his/her designee.

The AESI Report Form must be completed in accordance with the AESI Report Form Completion Guidelines. If all information on the AESI Report Form is not available at the time of the initial report, follow-up AESI reports will be completed and submitted.

To report an AESI, complete and send the AESI Report Form to the following:

Theravance Biopharma Clinical Safety

[REDACTED]

For medical questions regarding an AESI, contact the medical monitor by telephone as follows:

Medical Monitor Contact Information:

[REDACTED]

#### 7.2. Clinical Laboratory Abnormalities and Other Abnormal Assessments as Adverse Events or Serious Adverse Events

Abnormal laboratory findings (such as chemistry, hematology, or urinalysis) or other abnormal assessments (such as ECGs, x-rays, or vital signs) that are associated with signs and/or symptoms or are considered clinically significant in the judgment of the Investigator must be recorded as AEs or SAEs if they meet the definition of an AE (or SAE), as described in Section 7.1.1 (Adverse Event) and Section 7.1.2 (Serious Adverse Event).

If there are any AE questions, the Investigator is encouraged to contact the sponsor to discuss.

#### 7.3. Assessment of Adverse Events

All AEs will be assessed by the Investigator and recorded in the CRF, including the dates of onset and resolution, severity, relationship to study medication, outcome, and action taken with study medication.

### 7.3.1. Severity

The term “severe” is often used to describe the intensity (severity) of a specific event (as in mild, moderate, or severe myocardial infarction); the event itself, however, may be of relatively minor medical significance (such as severe nausea). This is not the same as “serious,” which is based on subject/event outcome or action criteria usually associated with events that pose a threat to a subject’s life or functioning. The severity of AEs will be assessed according to the following definitions:

- **Mild:** The AE is noticeable to the subject and/or the Investigator but does not interfere with routine activity.
- **Moderate:** The AE interferes with routine activity but responds to symptomatic therapy or rest.
- **Severe:** The AE significantly limits the subject’s ability to perform routine activities despite symptomatic therapy.

### 7.3.2. Causal Relationship to Study Medication

The Investigator’s assessment of causality is based on clinical judgment regarding the reasonable possibility that the study medication caused the event and may include consideration of some or all of the following factors:

- Possible alternative causes of the AE, including the disease under treatment, comorbid conditions, other medications, and environmental factors.
- The temporal association between drug exposure and onset of the AE.
- Whether the clinical or laboratory manifestations of the AE are consistent with known actions or toxicity of the study medication.
- Whether the AE resolved or improved with decreasing the dose or stopping the study medication (“de-challenge”) or recurred or worsened upon re-exposure to the study medication (“re-challenge”).

The causal relationship between the study medication and the AE will be described using one of the following categories:

- **Not Related:** Evidence exists that the AE has an etiology other than the study medication (such as a preexisting condition, underlying disease, intercurrent illness, or concomitant medication).
- **Related:** A temporal relationship exists between the event onset and administration of the study medication. It cannot be readily explained by the subject’s clinical state or concomitant therapies and appears with some degree of certainty to be related based on the known therapeutic and pharmacologic actions of the drug. In case of cessation or reduction of the dose, the event abates or resolves and reappears upon re-challenge. It should be emphasized that ineffective treatment should not be considered as causally related in the context of AE reporting.

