The subject will receive an assessment of their physical condition, including safety and laboratory evaluations and related aspects of their disease states according to the Schedule of Study Procedures (Table 1). The presence of symptomatic nOH symptoms and reported sensation of dizziness, lightheadedness, feeling faint, or feeling like blacking out (OHSA#1) must be confirmed by the application of a tilt-table test. This tilt-table test serves 2 purposes: (i) determination of the systolic/diastolic BP (DBP) changes, and (ii) training the subjects to recognize the sensations associated with OHSA#1.

Eligible subjects will undergo training of accurate scoring of their sensation of dizziness, lightheadedness, feeling faint, or feeling like blacking out as outlined by the OHSA#1.

Following the screening period, the subject will proceed to Visit 2 to further confirm the additional eligibility criteria prior to randomization. This includes the completion of the Orthostatic Hypotension Questionnaire (OHQ) in which a minimum score of 4 points in OHSA#1 is required. Subjects meeting all applicable inclusion criteria and none of the applicable exclusion criteria, including confirmation of relevant criteria by the independent Enrollment Steering Committee (ESC), will be randomized to receive either TD-9855 or matching placebo for the next 4 weeks.

Following randomization and completion of study assessments, the subject will receive a [REDACTED] dose of TD-9855 (or matching placebo) once daily (QD) for the remaining double-blind treatment period.

Weekly assessments will be conducted as outlined in the Schedule of Study Procedures (Table 1). Refer to the footnotes in Schedule of Study Procedures for a description of all assessments. Refer to Appendix 9 and the Study Reference Manual for detailed instructions for conducting subject assessments in clinic and remotely. These instructions have been provided to ensure the method and conduct of each assessment is consistent across sites and subjects for both in clinic and remote visits.

Discontinuation of subjects may occur at any time. Dose stopping criteria include meeting at least 1 of the following rules:

- [REDACTED]
- [REDACTED]
- [REDACTED]
- [REDACTED]

No dose reduction is permitted at any time.

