## 6.8. Discontinuation

### 6.8.1. Dose Stopping Rules

Any subject meeting 1 or more of the following stopping criteria will be required to immediately discontinue dosing with study medication and subsequently subject will be discontinued from participation in the study:

- [REDACTED]
- [REDACTED]
- [REDACTED]
- [REDACTED]

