### **7.4.3. Serious Adverse Event and Adverse Event of Special Interest Reporting Timeline**

All SAEs and AESIs must be reported to Clinical Safety and Pharmacovigilance within 24-hours of the time the Investigator or his/her designee becomes aware that an SAE or AESI has occurred, whether or not the event is considered to be related to study medication. If the initial SAE or AESI is reported by telephone, a written report signed by the Investigator must be submitted within 24-hours.

The SAE/AESI Report Form must be completed in accordance with the SAE/AESI Report Form Completion Guidelines. If all information on the SAE/AESI Report Form is not available at the time of the initial report, follow-up SAE or AESI questionnaires will be completed and submitted.

To report an SAE or AESI, complete and send the SAE/AESI Report Form to the following:

Theravance Biopharma Clinical Safety

[REDACTED]

For medical questions regarding an SAE or AESI, contact the medical monitor by telephone as follows:

Medical Monitor Contact Information:

[REDACTED]

For fatal or life-threatening events, also fax copies of hospital case reports, autopsy reports, and other documents when requested. Additional information may be requested from the Investigator to ensure the timely completion of accurate safety reports.

An SAE may qualify for reporting to regulatory authorities if the SAE is possibly attributable to the study medication and is unexpected/unlisted based on the current TD-9855 IB. In this case, all Investigators will receive notification of the event. The Investigator is responsible for notifying the Institutional Review Board or Ethics Committee and documenting the notification, as required by local regulatory authorities and in accordance with the local institutional policy.

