9.1. Adverse Events

Adverse events are collected from signing of the informed consent through the end of follow-up. Adverse events will be coded to the preferred terms of the Medical Dictionary for Regulatory Activities (MedDRA®, version 24.0).

A treatment-emergent adverse event (TEAE) will be defined as any AE that begins on or after the date of first dose of study drug up to 14 days after the date of last dose of study drug. However, for patients who continued into Study 0170, any AE occurs after Study 0170 Visit 1 (Study 0169 Visit 6) will be considered as a TEAE for Study 0170 and will not be included in the AE summary for Study 0169 to avoid double counting.

AEs observed during the period from obtaining informed consent to the start of administration of study drug will not be considered as TEAEs and will be listed only.

AEs and TEAEs will be listed by subject. In addition, subjects with AEs leading to permanent or temporary discontinuation of treatment will be listed separately.

TEAEs will be summarized overall with counts and percentages of subjects with the events, by treatment group, system organ class, and preferred term. TEAEs leading to permanent or temporary discontinuation of treatment, related to study treatment (i.e., any reported as related), serious TEAEs, frequent TEAEs (defined as >3% in the study population), TEAEs by severity, TEAEs of special interest, deaths, and TEAEs by maximum severity and causality will be summarized.

If no adverse events meeting a specific table criterion are observed, the summary table will indicate that there were no occurrences.

9.1.1. [REDACTED]

[REDACTED]

[REDACTED]

[REDACTED]

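### Protocol 7.3.2: the two causality categories do not follow the section's own reasonable-possibility standard and leave some permanently stopped events in neither category

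*Protocol*

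**What the plan says.** Protocol 7.3.2 opens by resting causality on the investigator's clinical judgment of a reasonable possibility. It lists factors of which some or all may be weighed, and the response to de-challenge or re-challenge is one of them.

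The section then requires a choice: "The causal relationship between the study medication and the AE will be described using one of the following categories". There are two.

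- Not Related: "Evidence exists that the AE has an etiology other than the study medication".
- Related: the timing fits, the event is not readily explained by the subject's condition or other therapies, and it "appears with some degree of certainty to be related based on the known therapeutic and pharmacologic actions of the drug". The definition continues: "In case of cessation or reduction of the dose, the event abates or resolves and reappears upon re-challenge".

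On dosing, the synopsis and Protocol 3.1 state: "No dose reduction is permitted at any time". Under Protocol 6.8.1 a subject who meets a stopping criterion is "required to immediately discontinue dosing with study medication and subsequently subject will be discontinued from participation in the study". Protocol 8.6.2, however, plans a listing of subjects whose treatment was temporarily interrupted for AEs, and SAP 9.1 summarizes TEAEs leading to temporary as well as permanent discontinuation.

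**The concern.** A binary causality call works only if the two categories are complementary and apply the same standard as the instruction that introduces them. Here the lead-in asks for a reasonable possibility, while each definition asks for more: Related for some degree of certainty and, after cessation, recurrence on re-challenge; Not Related for evidence of a different cause. An event can fall between them, and for an event that ended treatment the recurrence element cannot be observed in the study.

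At stake is consistent labelling. A site working from the lead-in and a site working from the definition can classify the same event differently. Protocol 7.4.2 sends investigators to 7.3.2 for the assessment, so this text is what they apply. Section 7.4.3 uses a further, looser expression for regulatory reporting: "An SAE may qualify for reporting to regulatory authorities if the SAE is possibly attributable to the study medication". The protocol thus words the causality threshold in more than one way.

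**Working it through.** The plan gives no figure on this point and no arithmetic applies. The check sets the texts side by side.

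**Inputs.** The lead-in and categories in Protocol 7.3.2; the bar on dose reduction in Protocol 3.1; the stopping consequence in 6.8.1; temporary interruption in 7.1.3, 8.6.2 and SAP 9.1; use of the label in 7.4.2 and SAP 9.1.

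**Step 1: are the two definitions complementary?** They would be if every event without evidence of another cause met Related. That fails in two ways.

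- An event with no evidence of another cause that does not match the drug's known actions meets neither definition. This does not depend on re-challenge.
- An event that meets the timing, alternative-explanation and known-action elements still has to satisfy the cessation sentence if dosing stopped.

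**Step 2: can the cessation sentence be met?** It depends on what happened to dosing.

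1. Dosing continued: the sentence is not triggered.
2. Dose reduced: this cannot arise, because reduction is barred.
3. Dosing interrupted and restarted: re-challenge can be observed, so Related can be met in full.
4. Dosing stopped permanently, including under 6.8.1: there is no re-exposure in the study. Protocol 3.1 opens Study 0170 only to subjects who complete the 4-week treatment period, so early stoppers are not re-exposed by that route either. Read literally, the sentence cannot be met.

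**Step 3: a constructed example of case 4.** An event begins soon after dosing, has no evident other cause, matches the drug's pharmacology, leads to permanent discontinuation and then resolves.

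- Lead-in: a reasonable possibility exists.
- Not Related: not met, because there is no evidence of another cause.
- Related: timing, absence of another explanation, pharmacology and abatement are met; reappearance on re-challenge is unobservable, so the definition is not met as written.

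The lead-in points to Related, yet neither definition is satisfied. For an event with lasting damage, such as the myocardial infarction or cerebrovascular accident listed as AESIs in 7.1.4, abatement followed by reappearance is hardly a workable test.

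**Step 4: what uses the label?**

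- SAP 9.1: the summary of related TEAEs and the summary by maximum severity and causality.
- Protocol 7.4.2: investigators may report SAEs assessed as related for 30 days after the last study visit. For subjects not entering Study 0170 that visit is two weeks after the last dose, so the window runs to about 14 + 30 = 44 days after the last dose. Dosing has already ended throughout it.

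**Step 5: what does not use it?** Protocol 7.4.2 records all AEs whatever their causality. Protocol 7.4.3 requires SAEs and AESIs within 24 hours regardless of relationship. SAP 9.1 summarizes TEAEs leading to discontinuation, serious TEAEs, TEAEs of special interest and deaths separately from related TEAEs.

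**The case against.** The strongest reply is that one sentence should not be read apart from its section. The lead-in governs, re-challenge is an optional factor there, and 7.4.2 calls 7.3.2 guidelines. An investigator may therefore record Related for an event that ended treatment. The sentence can also be read as saying only that the event would recur if re-challenge took place. This stands as far as it goes: the text is inconsistent rather than prohibitive. It does not cure the inconsistency, because the two readings give different labels for the same event, and the known-action gap in Step 1 remains on either reading.

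A reader might also infer more than the documents support:

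- *That the dose rules exclude re-challenge altogether.* Only reduction is barred. Temporary interruption is foreseen in Protocol 7.1.3 and 8.6.2 and in SAP 9.1, so events followed by interruption and restart can meet the full definition.
- *That the rule pushes the most important events away from Related.* No direction is shown. An investigator with a plausible temporal link and no other cause lacks a textual basis for Not Related too, and may well choose Related.
- *That serious events would go unreported or untabulated.* Step 5 shows otherwise. Protocol 6.8.4 also provides for periodic unblinded safety review by an independent committee, and the regulatory-reporting wording in 7.4.3 is looser than the Related definition.

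**Conclusion.** The point holds in limited form. Protocol 7.3.2 states one standard and then defines its two mandatory categories by others, and those categories are not exhaustive. The re-challenge element fails, on a literal reading, for events followed by permanent discontinuation; the dose-reduction branch is empty. An event of that kind with plausible timing and no evidence of another cause literally meets neither definition.

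The effect is possible inconsistent labelling in the descriptive related-TEAE summaries and in an optional reporting window. No efficacy analysis is touched, and SAP section 9 generally plans no inferential tests on safety data. The number of events cannot be derived: the documents give no expected counts, and the criteria in 6.8.1 are redacted, so the events they cover and any restart provision among them cannot be seen. The conclusion assumes a literal reading of the category text and no re-exposure within the study after permanent discontinuation.

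**What to change.** In Protocol 7.3.2, make the two categories complementary and build them on the section's opening standard:

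- Related: there is a reasonable possibility that the study medication caused the event.
- Not Related: there is no such reasonable possibility.

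Remove the sentence on abatement and re-challenge from the Related definition. De-challenge and re-challenge already stand in the factor list and should remain there as supportive evidence where available. Carry the same wording into the CRF completion guideline.

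The cost is a wording change and a site memo, and possibly some events classified differently. No dose, interruption or stopping rule changes.
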